At W000, the investigator will check that the RU area measured centrally at ASSE is consistent with his/her measurement, that independent experts validation is done, and will re check the selection criteria.

- If the central measurement of ASSE RU area is not fitting the selection criteria, the participant will not be included.
- If the central measurement of ASSE RU area confirm the RU area selection criteria, the investigator will check that the participant complies with the inclusion criteria, the recommendations for compression (stockings wearing $\geq 80\%$ of the time according to diary information) and is compliant with placebo selection treatment (between 80 and 120%). The relative change of RU area compared with the RU area measured at ASSE visit must be less or equal to 20% in order for the participant to be eligible for inclusion. This relative change calculated centrally will be used to check the compliance with the inclusion criteria.
- Patients found to be eligible for randomisation will have a 3D picture of the RU on the day of W000, taken after randomisation and after wound bed preparation. This picture (W000-B) will be the baseline measure for comparison with all subsequent pictures taken at following visits.

All participants found to be eligible for inclusion will be randomised to one of the following six groups - S42909 100, 200, 400, 800 or 1200 mg per day - or placebo. The randomisation will be performed using a centralised, dynamic, balanced with 1:1:1:1:1 ratio, stratified randomisation according to the country, a combined prognosis criterion (age and size of ulcer, using the RU area measured centrally at W000), and diabetic status (yes/no) by the IWRS. For stratification purposes, will be considered diabetic patients those with an already

confirmed diagnosis of diabetes as well as previously unknown diabetic patients with a fasting blood sugar ≥ 7 mmol/L and/or an elevated HbA1c value between 6.5 and 8% on pre-inclusion laboratory results.

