Document title

STATISTICAL ANALYSIS PLAN (SAP)

ATTACHED TO CL2-42909-016 STUDY

Study title

Dose-response relationship study of S42909 on leg ulcer healing after oral repeated administration in patients with active venous leg ulcer. A 10-week randomised, double-blind, placebo-controlled, prospective, international, multicentre, phase IIa study.

Test drug code

S42909

Indication

Venous leg ulcer

Development phase

IIa

Protocol code

CL2-42909-016

EudraCT Number

2016-004143-36

Universal Trial Number

NA

Sponsor

ILKOS THERAPEUTIC INC.

Date of the document

02 March 2020

Version of the document

1.0

CONFIDENTIAL

Signatories

Prepared by:

[name]
Biostatistician
Keyrus BioPharma – FRANCE

[figure not shown]
Signature

Date

02/03/2020

[name]
Biostatistician
I.R.I.S. – FRANCE

02/03/2020

Approved by:

[name]
Biostatistics Project Manager
I.R.I.S. – FRANCE

Signature

Date

[figure not shown]
02.03.2020

[name]
President and CEO
Ilkos Therapeutic Inc.

[figure not shown]
02/03/2020

[name]
Chief Medical Officer
Ilkos Therapeutic Inc.

[figure not shown]

02/03/2020

[name]
C.T.I.
I.R.I.S. – FRANCE

02/03/2020

Follow up of versions

Version	Release date (dd/mm/yyyy)	Key modifications (*)	Impact
1.0	02/03/2020	The linear advance of the wound margin towards the wound center will not be described as a relative change from baseline, as the value at baseline of the linear advance is equal to zero by definition. Only value at each visit will be provided.	No impact
		Additional subgroup : Size of the ulcer at baseline ($\leq 20 \text{ cm}^2$ / $> 20 \text{ cm}^2$)	No impact
		Randomised set definition: Only patients included will be considered.	2.1 Analysis sets
		MCPMod adjusted on diabetic factor and prognosis criteria on size and age of the ulcer at baseline will be provided as sensitivity analysis	3.4.2.2 Sensitivity analyses
		The primary analysis will be repeated in the FAS with patients from centers where PK results confirm the treatment intake.	3.4.2.2 Sensitivity analyses
		The number, dose and/or duration of analgesic drug for Venous Leg Ulcer (VLU) will not be described. The analgesic description will be done only through the question “Need to take medication for control of the pain associated with VLU?” from the pain questionnaire	3.4.3 Secondary efficacy criteria

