1.3. Determination of sample size

Sample size was estimated with a type one error rate set at 2.5% and using the statistic function “sampszie” described in the publication “MCPMod: An R Package for the Design and Analysis of Dose-Finding Studies” edited by B. Bornkamp, J. Pinheiro and F. Bretz (2009).

Considering:

- A standard deviation of 42%.
- A minimal relative change of Reference ulcer area at 4 weeks (Rmin) of 32.5%.
- A maximal relative change of Reference ulcer area at 4 weeks (Rmax) of 62.5%.
- A maximal efficacy (Rmax – Rmin) of 30%.
- Six doses: 0 (placebo), 100, 200, 400, 800, 1200 mg per day.
- Seven candidate models defined by some couples (d*, p*) (dose, maximal percentage of efficacy):
 - Linear.
 - Emax1 (200 mg, 90%).
 - Emax2 (400 mg, 70%).
 - Sigmoid Emax (200 mg, 10%) and (1000 mg, 90%).
 - Logistic (200 mg, 10%) and (1000 mg, 90%).
 - Exponential1 (400 mg, 10%).
 - Exponential2 (800 mg, 10%).

Candidate models are presented in [Figure \(1.3\) 1](#).

Figure (1.3) 1 - Dose response models

- Function “min” of Bretz package (power of each model is greater or equal to the nominal power to detect a signal of dose-response relationship).

27 evaluable participants per group guarantee a nominal power of at least 80% to detect a signal of dose-response relationship (proof-of-concept).

After 1000 data simulations based on above hypotheses, with a true dose-response relationship supposed to be a logistic model (defined by the couples (200 mg, 10%) and (1000 mg, 90%)) and 27 participants by dose, the empiric power to detect a signal of dose-response relationship (main objective) is about 90%.

Taking into account an exclusion rate from the Randomised Set (RS) estimated at 20%, about 34 participants per treatment group had to be included.

Based on that exclusion rate, a total of 204 patients was planned to be included in the study. Due to recruitment difficulties, 121 patients were finally included in the study.

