3.1.2. General definitions

The following definitions will be considered:

- **IMP** is the treatment intake (S42909 or Placebo) post randomisation.
- **Analysable value** will be defined as any non-missing value.
- **Baseline value** will be defined as the last analysable value prior to the first IMP intake (*i.e.* before or the same date as the first IMP intake date).
Note: In case of patient included and/or randomised but not treated (*i.e.* patients with treatment duration equal to 0): value at baseline is defined as the last analysable value prior or equal to the date of the inclusion visit.
- **Post-baseline value** will be defined as any value recorded at a given timepoint after baseline.
- **Change from baseline** will be defined as the arithmetic difference between a post-baseline value and the baseline value for a given variable at a given time point.
- **Relative change from baseline** will be defined as : $100 * \text{change from baseline} / \text{baseline value}$.

For safety criteria (except for adverse events), the following definitions will be applied:

- A value is considered under treatment if the assessment date is between the first IMP intake date (excluded) over the W000 and W006 period and the last IMP intake date "+ 15 days" (included).

Note: for all definitions concerning value under treatment '+ 15 days' was calculated according to the half-life of the S42909.

- High emergent abnormal value under treatment according to the laboratory reference ranges is defined as value \leq ULN (Upper Limit of Normal laboratory reference range) or missing at baseline and $>$ ULN under treatment.
- Low emergent abnormal value under treatment according to the laboratory reference ranges is defined as value \geq LLN (Lower Limit of Normal laboratory reference range) or missing at baseline and $<$ LLN under treatment.

- High emergent abnormal value under treatment according to the cut-offs for PCSA (Potentially Clinically Significant Abnormal value) values is defined as value \leq ULS (Upper Limit used to define potentially clinically Significant abnormal values) or missing at baseline and $>$ ULS under treatment.
- Low emergent abnormal value under treatment according to the cut-offs for PCSA values is defined as value \geq LLS (Lower Limit used to define potentially clinically Significant abnormal values) or missing at baseline and $<$ LLS under treatment.

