- $S^2 = \sum_{i=1}^k \sum_{j=1}^{n_i} \frac{(Y_{ij} - \bar{Y}_i)^2}{N - k}$
- c_m is the vector of contrasts with $\sum_{i=1}^k c_{mi} = 0$

The dose-response tests identify the set of clinically relevant models. A multiplicity adjustment is taken into account in the MCP-step. The joint distribution of the m test statistics is taken into account to compute an adjusted critical value that defines the threshold for statistical significance.

Under the global null hypothesis of no treatment effect under any model, the test statistics follow a central multivariate t distribution with $N - k$ degrees of freedom and correlation matrix R . More details for matrix R are given in Appendix 5.3.1.

To derive the multiplicity-adjusted critical value, denoted by q , let $T_1; \dots; T_m$ denote the random variables that have the same joint distribution as $t_1; \dots; t_m$ under the global null hypothesis. The adjusted critical value q is found from :

$$\Pr(T_{max} > q) = \alpha$$

Where α is the pre-specified Family Wise Error Rate (FWER) level equal to 0.025 (one-sided test).

The set of clinically relevant dose-response model corresponds to the models associated with $t_i > q$. The adjusted p-value will be calculated according to the value of q .

Among the set of clinically relevant dose-response models, the best dose-response contrast will be identified as the contrast test with the maximum test statistics.

An estimation of parameters of the best model selected will be provided according to the observed data as well as a plot of this model.

If relevant, modelisation will be done even if no dose-response model is significant.

Multiplicity issues:

The multiplicity issue due to multiple dose-response models is corrected with the computation of an adjusted critical value and adjusted p-values.

Missing data handling: missing data will not be imputed.

Statistical elements:

Finally, the following elements will be provided in summary tables:

- Descriptive statistics and 95% CI of the primary criterion in each arm.
- The best dose-response selected.
- An estimation of parameters of the best model selected.

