3.4.2.2. Sensitivity analyses

- The MCPMod method adjusted on diabetes status factor and prognosis criteria on size and age of the ulcer factor will be applied to the primary efficacy endpoint in the FAS. Details of the MCPMod approach with covariate-adjusted inferences are provided in Appendix 5.3.2.
- The primary analysis will be repeated in the FAS with patients from centers where PK results confirm the treatment intake.

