5.3.2. MCPMod method with covariate-adjusted inferences

The MCPMod method was originally introduced for developing robust dose-response evaluation strategies in Phase II trials with simple primary analyses, e.g., analyses without covariate adjustment ([Bretz, Pinheiro and Branson, 2005](#)). The original method was later extended in multiple directions. [Pinheiro et al. \(2013\)](#) demonstrated how a generalized version of the MCPMod approach can be set up to enable covariate-adjusted inferences in the primary analysis.

The general MCPMod method proposed in [Pinheiro et al. \(2013\)](#) will be applied to the primary endpoint in the FAS. This endpoint is assumed to be normally distributed and will be analyzed using an analysis of covariance (ANCOVA) model adjusted for two stratification factors (combined prognosis criteria and diabetic status).

The general MCPMod method will be applied to the seven pre-defined dose-response models (see definition in [Table \(5.3.2\) 1](#)) with the 6 doses. The models will be denoted by $f_i(d, \beta)$, $i = 1 \dots, 7$, where d is the dose and β is a vector of model parameters, and the doses will be denoted by d_1, \dots, d_6 .

The method will be implemented as follows. As the very first step, initial values of the model parameters will be selected for the pre-defined models. The column vector of initial values for the i th model will be denoted by b_i , $i = 1 \dots, 7$. Let μ_i denote the column vector of mean effects computed from the i th model using these initial values of the model parameters, i.e., $\mu_{ij} = f_i(d_j, b_i)$, $i = 1 \dots, 7$, $j = 1 \dots, 6$.

The ANCOVA model without an intercept adjusted for the two stratification factors will be fitted to the data. Let $\hat{\mu}_j$ denote the covariate-adjusted mean effect in the j th dose group, $j = 1 \dots, 6$, and let $\hat{\mu}$ denote the column vector of covariate-adjusted mean effects. Also, let S denote the covariance matrix for these mean effects estimated from the ANCOVA model.

The optimal dose-response contrasts will be found by computing the following set of vectors:

$$c_i = S^{-1} \left(\mu_i - \frac{\mu'_i S^{-1} I}{I' S^{-1} I} \right),$$

where the prime denotes transposition and I is a column vector of 6 ones, i.e., $I' = (1 \ 1 \ 1 \ 1 \ 1 \ 1)$. After that each vector is normalized, i.e., $c_i = c_i / |c_i|$. The resulting column vector c_i is the optimal dose-response contrast for the i th model, $i = 1 \dots, 7$.

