Let C denote the contrast matrix created from the model-specific optimal contrasts and define the matrix D as $D = C' S C$. This matrix is the covariance matrix for the optimal contrasts. The test statistic for assessing the significance of the optimal contrast based on the i th model is given by

$$t_i = \frac{c'_i \hat{\mu}}{c'_i S c_i}, i = 1 \dots, 7.$$

These test statistics follow a multivariate t distribution with an infinite degrees of freedom and correlation matrix $A^{-1} D A^{-1}$, where $A = \sqrt{\text{diag } D}$, i.e., A is a diagonal matrix constructed by finding the diagonal elements of D and computing the square root.

The set of significant dose-response models is selected by comparing each test statistic to an adjusted critical value q . This critical value is found from the joint distribution of the test statistic under the global null distribution of no dose-response effect for any of the seven pre-defined models. In other words,

$$P(\max(t_1, \dots, t_7) \geq q) = \alpha,$$

where α is a one-sided Type I error rate ($\alpha = 0.025$).

If the set of significant dose-response models is non-empty, the best dose-response model is chosen as the model corresponding to the most significant test statistic. Let k denote the index of the best dose-response model.

Once the best dose-response model is identified, it is fitted to the covariate-adjusted mean effects using the method of weighted least squares (WLS), i.e., the model is fitted by minimizing the following WLS criterion

$$(\hat{\mu} - f_k(d, \beta))' S^{-1} (\hat{\mu} - f_k(d, \beta))$$

with respect to the vector of model parameters β .

If relevant, modelisation will be done even if no dose-response model is significant.

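### The primary MCPMod ignores ulcer prognosis class and diabetic status, although allocation is minimised on both; the SAP's own adjusted MCPMod should be primary, with IWRS values and residual degrees of freedom

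*SAP*

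**What the plan says.** SAP 1.2.2 describes minimisation on country, combined prognosis class (size and age of ulcer) and diabetic status. Protocol Section 2 introduces these factors after stating that wound care and baseline ulcer characteristics influence healing.

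The primary model in SAP 3.4.2.1 is Y_ij = μ_i + ε_ij. It has no covariate and a variance pooled within dose, and "the test statistics follow a central multivariate t distribution with" N − k degrees of freedom. Protocol 10.1.4 likewise plans contrast tests and names no covariates.

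The adjusted method is in SAP 3.4.2.2: "The MCPMod method adjusted on diabetes status factor and prognosis criteria on size and age of the ulcer factor will be applied" as a sensitivity analysis. SAP 5.3.2 gives the details: the endpoint "will be analyzed using an analysis of covariance (ANCOVA) model adjusted for two stratification factors", namely prognosis class and diabetic status. For the reference distribution it says: "These test statistics follow a multivariate t distribution with an infinite degrees of freedom". Country is in neither model.

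SAP 1.3 reports the outcome of recruitment: "Due to recruitment difficulties, 121 patients were finally included in the study", against 204 planned.

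**The concern.** Balancing arms on prognostic factors and then leaving those factors out of the test has a known effect. Minimisation removes most of the between-stratum variation from the arm comparisons, but the pooled variance S² still contains it. The standard error is then too large, the true error rate falls below 2.5%, and power is lost. False positives are not inflated.

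With recruitment stopped at 121, adjustment is one of the few ways left to recover power from data already collected, and the SAP has already written the method.

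Two details of that method need attention wherever it ranks. Infinite degrees of freedom do not match the N − k rule of the primary test. The source of the covariates is also not stated, so classes re-derived for analysis could replace the ones used for allocation.

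**Working it through.** **Inputs from the documents.** One-sided α 2.5%; SD 42; doses 0, 100, 200, 400, 800, 1200 mg; seven candidate models with the parameters of SAP Table (5.3.1) 2; 27 evaluable per arm for at least 80% power; 20% exclusion; 121 included.

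**Assumptions.** The documents give no R². Total R² of 0, 0.10, 0.20 and 0.30 is assumed, split equally over the three minimisation factors, so the two adjusted factors carry two thirds. The simulation also assumes nine countries with shares of 3–25%, 60% in class B, 20% diabetic and a biased coin of 0.8. It uses 4,500 minimised allocations with 40 outcome draws each (Monte Carlo SE about 0.15 point for power and 0.04 for error).

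**1. Reproduce the plan.** Power for model m is P(max_l T_l > q), where T is multivariate t with noncentrality c_l′μ_m √n / σ. Example, linear model with its own contrast: the dose deviations from 450 have sum of squares 1,075,000, so c′μ = 0.025 × √1,075,000 = 25.92. The noncentrality at n = 27 is 25.92 × 5.196 / 42 = 3.21. Over all seven contrasts and models, minimum power at 27 per arm is 81.6%, in line with the stated 80%.

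**2. Actual numbers.** 121 × 0.8 = 96.8, so 97 evaluable. The linear noncentrality falls to 25.92 × √(97/6) / 42 = 2.48. Simulated minimum power of the unadjusted test is 58.2% at 97 and 68.8% if all 121 are evaluable (R² = 0). This fall comes from recruitment alone.

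**3. Effect of adjustment.** Let r² be the share explained by prognosis class and diabetes. The residual SD is 42√(1 − r²): 40.58, 39.10 and 37.57 for r² = 0.067, 0.133 and 0.20. The df are N − 8 (six dose means and two binary factors), that is 89 at 97.

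| Total R² | 0 | 0.10 | 0.20 | 0.30 |
|---|---|---|---|---|
| Unadjusted minimum power, 97 (%) | 58.2 | 57.9 | 57.6 | 57.1 |
| Adjusted minimum power, 97 (%) | 57.8 | 61.1 | 64.6 | 68.4 |
| Difference (points) | −0.4 | +3.2 | +7.0 | +11.3 |
| Unadjusted minimum power, 121 (%) | 68.8 | 68.8 | 68.7 | 68.7 |
| Adjusted minimum power, 121 (%) | 68.7 | 71.9 | 75.3 | 78.9 |
| True one-sided error, unadjusted, 97 (%) | 2.5 | 2.0 | 1.6 | 1.2 |
| True one-sided error, adjusted, residual df, 97 (%) | 2.5 | 2.4 | 2.2 | 2.0 |

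Direct multivariate-t calculation with the same residual SDs gives 61.3, 64.8 and 68.4% at 97, which agrees. In sample-size terms, 1/(1 − r²) is 1.07, 1.15 and 1.25: about 7, 15 and 25% more patients. If country is not prognostic and the two factors carry all the R², adjusted power is 62.6, 68.1 and 74.1%, against 57.6, 57.1 and 56.4% unadjusted.

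**4. Degrees of freedom.** The critical value is 2.415 at 89 df and 2.374 at infinite df. Using the latter gives a true error of 2.7% when R² = 0, and 2.7% throughout if country is not prognostic.

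**5. Covariate source.**
- *Diabetes.* The allocation definition (SAP 1.2.2) includes fasting glucose ≥ 7 mmol/L; the efficacy definition (SAP 5.2.3) does not. HbA1c is tested in everyone except known diabetics with a recent acceptable result (Protocol 8.2). Barring IWRS entry errors and coding gaps, the two differ only for a patient with high glucose, HbA1c < 6.5% and no coded diabetes history.
- *Ulcer size.* Allocation uses "a combined prognosis criterion (age and size of ulcer, using the RU area measured centrally at W000"). That measurement comes from a picture taken 3 or 4 working days earlier (Protocol 7.1). The SAP version table says: "MCPMod adjusted on diabetic factor and prognosis criteria on size and age of the ulcer at baseline will be provided as sensitivity analysis". A baseline value "will be defined as the last analysable value prior to the first IMP intake" (SAP 3.1.2), which would be the W000-B picture taken after randomisation and before the first dose. This suggests, but does not establish, that W000-B supplies the class. Using it would still be valid, but it would match the allocation less closely.
- *Ulcer age.* SAP 5.2.1 derives the duration class from the physician's date, for the subgroup analysis.

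If 2% of patients change prognosis class and 2% lose the diabetic label, the cost is 0.4, 0.8 and 1.4 points at R² 0.10, 0.20 and 0.30. With 5% and 5% it is 1.0, 1.9 and 3.0 points.

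**6. Country.** Adding pooled country to the two factors changes power by −0.8, +0.3, +1.6 and +3.2 points over R² 0 to 0.30, and by about −0.8 at every R² if country is not prognostic.

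**The case against.** The unadjusted primary is valid, follows the protocol and matches the sample-size basis, which uses a total SD of 42% with no covariate. The adjusted analysis is already pre-specified, so only its rank is in dispute. The gain rests on an R² that the documents do not give: it is 3.2 points at 0.10, and even at 0.30 power reaches only 68.4% with 97 patients. Protocol Section 2 gives a reason for country and for ulcer characteristics but none specific to diabetes, yet country would stay optional. The df excess is small. If country is also prognostic, the infinite-df error is about 2.65, 2.4 and 2.1% at R² 0.10, 0.20 and 0.30, so it falls below the nominal level in the last two cases. The SAP does call the covariates stratification factors. Re-ranking would also alter the PPS and PK-confirmed-centre repeats and the MED.

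Most of this stands as a limit on size. It does not remove the point: the possible loss is 0.4 point, the possible gain is several points, and the factors were chosen by the sponsor for allocation. Country is left optional because its computed gain is small and can be negative. The repeats follow whichever analysis is primary. The MED needs explicit wording.

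**Conclusion.** The concern holds as an efficiency point, not as a bias or false-positive problem. With 97 evaluable patients, adjusting for the two factors changes minimum power by −0.4 to +11.3 points over total R² from 0 to 0.30 under the equal split, and by up to 17.7 points (56.4 to 74.1%) if the two factors carry all of an R² of 0.30. The unadjusted test's true one-sided error falls to between 2.0 and 1.2% for R² 0.10 to 0.30. These sizes depend on the assumed R², its split and the simulated allocation; the direction does not, provided the factors are prognostic. Adjustment does not restore the planned 80% at 97 patients under the equal split. The df correction is small but needed for the stated 2.5%. The covariate-source question has little numerical effect and is settled by one sentence.

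**What to change.** Before the blind is broken, and recorded in the SAP version table as a change from the protocol:

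1. Make the ANCOVA-based MCPMod of SAP 5.3.2 the primary analysis and keep the unadjusted protocol analysis as supportive.
2. In 3.4.2.2 and 5.3.2 add: *Prognosis class and diabetic status are the values used by the IWRS at randomisation.*
3. In 5.3.2 replace infinite df by the ANCOVA residual df, N − 8 (89 at 97 evaluable).
4. In 5.3.2 confirm that the denominator of t_i is the square root of c′Sc. The text as extracted shows no root, which may be a reading artefact.
5. In 3.4.2.3 state that the MED uses the weighted least-squares fit of 5.3.2, and how L(d) and the bootstrap interval are obtained from it.

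A further sensitivity analysis adding country, with small countries pooled, is optional. If the sponsor keeps the protocol primary, items 2 to 4 still apply to the sensitivity analysis.

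The cost is two residual degrees of freedom, at worst 0.4 point of minimum power at 97 evaluable (58.2 to 57.8%), and a documented change to a protocol-defined primary analysis. No new data are needed.

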Participants will start a 14-days placebo selection treatment period to check their compliance with the IMP treatment and compression stockings, then start a 6-weeks IMP treatment being randomised equally in each treatment group (one dose or placebo) taking into account stratification factors. Finally, the participants will be followed-up during 2 weeks after the last intake of study treatment.

Patients will be assigned to one of the six treatment arms by an algorithm of randomisation meant to ensure balanced allocation in all respective arms of treatment. Participants in the optional PK will be randomised too, in order to ensure balanced allocation in all arms of treatment. Standard wound care treatment and baseline ulcer characteristics generally have a significant effect on progression of healing. Therefore it is planned to consider the following stratification factors:

- 1. Country - to account for the variation in wound care from one country to another
- 2. A prognostic factor for healing based on the wound characteristics (wound size and duration).
- 3. Diabetic status (yes/no)

Efficacy assessment

The evaluation of therapeutic response in patients with venous leg ulcers is difficult due to the long time needed to observe complete wound healing.

Whereas the complete healing remains the final goal for treating these patients ([Guidance FDA, 2006](#)), it would be of a great value to clinicians as well as to patients to have a reliable estimate of the time to total healing based on early progress in a given treatment regimen. This is especially important for chronic leg ulcers where the expected healing time with standard care may be 6 months or more. Today, the standard practice for the treatment of chronic wounds includes monitoring of the wound size at regular intervals.

A reliable qualification of the percentage of change in wound area over time is a significant prognostic measure of complete healing ([Kantor, 2000](#)). A study using a large cohort of venous leg ulcer patients has demonstrated that the percentage of change in wound area after 4 weeks of treatment can be a valid surrogate marker of healing at 12 or 24 weeks of care ([Gelfand, 2002](#)).

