1.2.2. Type of randomisation

The treatment randomisation and allocation are centralised using an Interactive Web Response System (IWRS) procedure. The treatment (S42909: 100, 200, 400, 800 or 1200 mg per day or placebo) is assigned at the inclusion visit (W000) by a dynamic, balanced with 1:1:1:1:1 ratio, stratified randomisation according to the country, a combined prognosis criteria (size and age of ulcer) and diabetic status (yes/no). The randomisation algorithm is built according to an adaptive randomisation by minimisation.

The combined prognosis criteria (size and age of ulcer) for ulcer healing are:

- A: $\leq 10 \text{ cm}^2$ and $\leq 6 \text{ months}$.
- B: $> 10 \text{ cm}^2$ or $> 6 \text{ months}$.

For the randomisation, the diabetic status is defined by known diabete and/or a fasting blood sugar $\geq 7 \text{ mmol/L}$ and/or elevated HbA1c value between 6.5% and 8% on pre-inclusion laboratory results.

Participants in the optional 24-hour PK analysis are distributed across treatment arms.

[figure not shown]

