5.2. Specific analytic definitions and data handling conventions

5.2.1. Disposition and baseline characteristics

Disease duration and reference ulcer duration

The disease duration according to the first leg ulcer (days) is defined as:

Date of selection visit (ASSE) – Date of diagnosis of the first leg ulcer

The reference ulcer duration according to the patient (days):

Date of selection visit (ASSE) – Date of occurrence or recurrence of the reference ulcer according to patient

The reference ulcer duration according to the physician (days):

Date of selection visit (ASSE) – Date of diagnosis or recurrence of the reference ulcer by the physician

Reference ulcer duration according to the physician will also be described in classes defined as:

If $(\text{disease duration (days)}/30.44) \leq 6$ then disease duration in class = ‘ ≤ 6 months’.

If $(\text{disease duration (days)}/30.44) > 6$ then disease duration in class = ‘ > 6 months’.

The reference ulcer duration according to the physician in classes is used for the **subgroup**.

CEAP classification (Clinical-Etiology-Anatomy-Pathophysiology)

Presence of an obstruction or a reflux in each type of veins (superficial veins and deep veins) will be derived with:

- **Superficial veins** will be defined as:

Telangiectasies or reticular veins; Great saphenous vein above knee; Great saphenous vein below knee; Small saphenous vein and Nonsaphenous veins.

- **Deep veins** will be defined as :
Inferior vena cava; Common iliac vein; Internal iliac vein; External iliac vein; Pelvic: gonadal, broad ligament veins, other; Common femoral vein; Deep femoral vein; Femoral vein; Popliteal vein Crural: anterior tibial, posterior tibial, peroneal veins (all paired) and Muscular: gastrocnemial, soleal veins, other.
- **Presence of an obstruction** is defined if the classification in (« Obstruction » or « Reflux and obstruction ») is completed.
- **Presence of a reflux** is defined if the classification in (« Reflux» or « Reflux and obstruction ») is completed.

Medical history other than studied disease and surgical or medical procedures history

The existence of a history (Yes/No) is defined from the presence, or not, of a Primary system organ class (SOC) and/or Preferred term (PT).

No specific medical and surgical histories or medical procedures are defined.

Previous treatments

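### The SAP's only covariate-adjusted analysis reduces ulcer size and age to one A/B class, although both are recorded on continuous scales

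*SAP*

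**What the plan says.** The primary MCP-Mod model (SAP 3.4.2.1) has a mean per dose and an error term, with no covariates. The adjusted version is a sensitivity analysis in SAP 3.4.2.2: "The MCPMod method adjusted on diabetes status factor and prognosis criteria on size and age of the ulcer factor". SAP 5.3.2 describes it as an "analysis of covariance (ANCOVA) model adjusted for two stratification factors (combined prognosis criteria and diabetic status").

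SAP 1.2.2 defines the prognosis criterion. Class A requires both an area of at most 10 cm² and an age of at most 6 months; failing either condition puts the patient in class B. Eligibility runs from 4.5 to 100 cm² at inclusion (Protocol 5.3) and from more than 6 weeks to less than 2 years of ulcer age at selection (Protocol 5.1.2).

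Both quantities exist on a continuous scale. Area is measured centrally by 3D imaging, and Protocol 4.2.1 says of the picture taken on the day of randomisation: "This picture (W000-B) will be the baseline measure for comparison with all subsequent pictures taken at following visits". SAP 5.2.1 derives reference ulcer duration in days, once from the patient's date and once from the physician's. The size splits at 20 and 50 cm² (SAP 3.4.4) are descriptive subgroups only.

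**The concern.** The protocol's own premise (section 2) is that "baseline ulcer characteristics generally have a significant effect on progression of healing". The adjusted analysis uses that premise in a coarse form. Class B pools a 5 cm² ulcer of 7 months with a 100 cm² ulcer of 23 months, and the ANCOVA treats the two as prognostically equal. Of size and age, the minimisation also balances only this class. A chance imbalance in area or duration inside class B is therefore handled neither by the allocation nor by the adjusted model.

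What is at stake is precision, and protection against such an imbalance, in a trial that included 121 patients instead of the planned 204 (SAP 1.3). The 20 and 50 cm² cut points added for description both lie above 10 cm². The plan thus looks for size differences within class B that its adjusted model cannot represent.

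**Working it through.** **1. The plan's own figure.** Inputs from SAP 1.3 and Table (5.3.1) 2: six doses, seven candidate shapes scaled to a maximal effect of 30, SD 42, one-sided 2.5%. With unit-length contrasts, the noncentrality is √n·c′μ/σ, and the maximum statistic is compared with the multivariate-t critical value (1,000,000 draws). At 27 per arm q = 2.40, the lowest power is 0.816 (Emax2) and logistic power is about 0.91. This agrees with the stated minimum of 80% and the roughly 90% under the logistic model. Also 27/(1 − 0.20) = 33.75, so 34 per arm and 204 in total.

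**2. Information kept by the class, by hand.** Assume log area and log duration are independent and uniform over the eligible ranges, each rescaled to (0, 1), and take 6 weeks, 6 months and 2 years as 42, 183 and 730 days.

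- Position of the area cut: a = ln(10/4.5)/ln(100/4.5) = 0.257.
- Position of the duration cut: b = ln(183/42)/ln(730/42) = 0.515.
- Class A share: p = ab = 0.133. Variance of the indicator: p(1 − p) = 0.115.
- Covariance with log area: p(a − 1)/2 = −0.0493. With log duration: p(b − 1)/2 = −0.0322.
- Squared correlation with log area: 0.0493²/(0.115/12) = 0.25. With log duration: 0.0322²/(0.115/12) = 0.11.
- Squared correlation with the equally weighted sum: (0.0493 + 0.0322)²/(0.115 × 2/12) = 0.35.

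So about 65% is lost with equal weights, 75% if only area matters and 89% if only duration matters. With independent covariates, no weighting keeps more than 0.25 + 0.11 = 0.36.

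**3. Sensitivity of that figure.** Simulation used truncated log-normal distributions over the eligible ranges: central area 8–20 cm² (log-SD 0.8), central duration 4–9 months (log-SD 0.7), correlation 0 or 0.3, and weights from area only to duration only. The loss was 51% to 96%, median 73%, and class A held 5% to 35% of patients. A true effect that is a step exactly at the A/B boundary gives zero loss. None of these inputs is in the documents.

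**4. Effect on power.** 121/6 ≈ 20 per arm. At the SAP's 20% exclusion rate this becomes 20.2 × 0.8 ≈ 16 evaluable. Assume size and duration on a continuous scale explain R² = 10% or 20% of endpoint variance, and that A/B keeps one third of that. The residual SD is 42√(1 − explained share).

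| Adjustment | Explained share | SD | Lowest power, 16/arm | Lowest power, 20/arm |
|---|---|---|---|---|
| None | 0 | 42.0 | 0.57 | 0.68 |
| A/B, R² 10% | 3.3% | 41.3 | 0.59 | 0.70 |
| A/B, R² 20% | 6.7% | 40.6 | 0.61 | 0.71 |
| Continuous, R² 10% | 10% | 39.8 | 0.62 | 0.73 |
| Continuous, R² 20% | 20% | 37.6 | 0.68 | 0.78 |

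Taking four covariate degrees of freedom from the error leaves the continuous rows unchanged to two decimals. SAP 5.3.2 refers the adjusted statistics to infinite degrees of freedom; that lowers the critical value slightly for every adjusted row and so does not affect the comparison between them.

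**The case against.** Adjusting for the factors used in the randomisation, in the form in which they were used, is coherent and common practice; nothing in SAP 5.3.2 is invalid. The analysis is also only a sensitivity analysis. The primary test is unadjusted, the MED uses the model selected by the primary test (SAP 3.4.2.3), and no success rule depends on the adjusted result. Prognosis is not ignored elsewhere: allocation is minimised on the class, the endpoint is relative to each patient's own baseline area, and the 20 and 50 cm² subgroups would show a size imbalance inside class B, though not correct for it. All of this stands, and it limits the point to a refinement.

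Three stronger readings are tempting, and the documents support none of them. A reader might take a loss of two thirds as a fact about this trial; it follows only from one set of assumed distributions and weights. A reader might infer that class A holds few patients; no document gives its share, and the assumed distributions above allow anything from 5% to 35%. A reader might conclude that the primary dose-response test or the MED is weakened by this choice; neither uses the adjusted model. The absence of any covariate from the primary model is a separate and larger matter.

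**Conclusion.** The point holds as an optional improvement. The one adjusted model carries size and age as a single indicator while better measurements of both are already in the database. Under a roughly log-linear effect at least half of their joint information is lost across the settings examined. The gain in lowest power is about 3 to 7 percentage points at either 16 or 20 patients per arm. It depends on the assumed R² of 10–20% and on the class keeping one third of the information. The other benefit, correcting imbalance inside class B, does not depend on those exact figures, but it does require that size or duration matter within that class. The trial's primary conclusion is unaffected either way.

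**What to change.** In SAP 3.4.2.2 and 5.3.2, keep the A/B class and diabetic status and add two continuous covariates to the ANCOVA:

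- log baseline reference ulcer area, from the W000-B picture. That picture was added by the March 2018 amendment, so for any patient without it use the baseline value as defined in SAP 3.1.2;
- log reference ulcer duration in days according to the physician (SAP 5.2.1). Name this variable explicitly, because that section defines two ulcer durations and writes the 6-month class rule in terms of disease duration.

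Also state whether the A/B class is the one held in the IWRS or one re-derived from baseline data. Signed change in area over the run-in could be added but is not needed: eligibility already limits it to 20%, and the protocol's formula (7.2) takes its absolute value.

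The cost is one model statement and two degrees of freedom. At 16 per arm the residual degrees of freedom go from 96 − 8 = 88 to 96 − 10 = 86. The contrasts are still built from the same candidate models, since the generalised method needs only adjusted means and their covariance matrix. The change should be fixed before unblinding; made afterwards, it should be labelled post hoc.
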